### **8.4 INFORMED CONSENT AND POINT OF ENROLLMENT**

The pre-operative and Surgery data will be collected retrospectively by performing a review of medical charts. Any patients identified as meeting the study eligibility criteria will then be consented for the study for the prospective observational data collection.

The IRB-approved informed consent document (ICD) will be presented and explained to each prospective subject by the Investigator or a delegated, trained clinical professional. Once the patient has had ample time to read the consent form, has been informed of all aspects of the study, and has had an opportunity to ask questions, the patient will be given a choice to voluntarily confirm his or her participation in the study as documented by completion of the informed consent document. After signing the ICD and the HIPAA (Health Insurance Portability and Accountability Act) authorization, the subject can then proceed with the study visits. The subject has the right to withdraw from the study at any time without consequences, as indicated in the ICD.

The subject's signed and dated informed consent must be obtained before conducting any study-specific procedures that are not part of the standard of care.

The investigative site must retain the original, signed written ICD. A copy of the written ICD must be given to the subject.

### **8.5 ELIGIBILITY AND STUDY ENTRY**

Subjects will be recruited from the Investigators' patient records. Eligible subjects will consist of those patients meeting all inclusion criteria and none of the exclusion criteria.

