	
To be included in the study, individuals must meet each eligibility criterion presented as follows:
 
 
1. Treated with the OMNI Surgical System in combination with cataract extraction [REDACTED] [REDACTED]. Two cohorts will be enrolled:             
 
a. Subjects who underwent a pre-operative washout of ocular hypotensive medications with post-washout DIOP of [REDACTED] OR
 
b. Subjects without a preoperative washout of ocular hypotensive medications with pre-operative medicated IOP [REDACTED] mmHg and on [REDACTED] hypotensive medications
 
 
 
 
Note: Mild to moderate open angle glaucoma as documented in subjects' medical record substantiated using funduscopic exam or OCT and at least one visual field test.
 
The visual field test may be historical (within 6 months prior to OMNI surgery).
 
 
2. Is able to understand study requirements and willing to follow study instructions
 
3. Is willing to return for required study follow-up visits
 

Exclusion Criteria	
The presence of any of the following characteristics will exclude individuals from study participation:
 
 
• Systemic disease that, in the opinion of the Investigator, would put the subject's health at risk and/or prevent completion of required study visits
 
• Ocular pathology which, in the Investigator's judgment, would either place the subject at increased risk of complications, contraindicate washout, place the subject at risk of significant vision loss during the study period (e.g., wet age macular degeneration (AMD), corneal edema, Fuch's dystrophy, active intraocular infection or inflammation within 30 days prior to Screening Visit, etc.), or interfere with compliance to elements of the study protocol (e.g., returning to Investigator's office for follow-up visits)
 
• Women of childbearing potential if they are currently pregnant or intend to become pregnant during the study period; are breast-feeding; or are not in agreement to use adequate birth control methods to prevent pregnancy throughout the study
 

Number of Subjects Enrolled and Treated	Up to 130 subjects will be enrolled
Number of Sites	Up to 15 study sites in US
Schedule of Visits	24 Month, 36 Month

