## 2 STUDY OBJECTIVE

The purpose of this study is to evaluate the long-term safety and effectiveness of the OMNI® Surgical System in subjects who were treated with the OMNI Surgical System in combination with Cataract Extraction, at least 700 days prior to enrollment.

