### **8.3 NUMBER OF SUBJECTS, DURATION OF FOLLOW-UP AND STUDY DURATION**

Up to 130 subjects will be enrolled. Eligible subjects will be enrolled at the 24-month follow up timepoint as shown by Table 1 or 2 as applicable. At least 50 subjects will be enrolled in each cohort. For subjects in cohort A, diurnal IOP measurements will be measured at both visits for those subjects who underwent medication washout and where DIOP was measured pre-operatively (Cohort A). Cohort A subjects using ocular hypotensive medication(s) at 24 and 36 months will undergo a medication washout (Table 3) and return for diurnal IOP measurements at a second visit within the same window, as shown in Table 1. There will be no diurnal IOP measurements for subjects in cohort B. IOP measurements will be measured as shown in Table 2.

It is anticipated that site initiation, recruitment and follow-up of subjects, data collection and site close-out will require approximately 60 months.

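### Patients are identified from the investigators' own charts about two or more years after surgery, with no visible rule to list or invite all eligible cases and no log of those passed over, so selection on known outcome is possible and could not be detected

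*Combined protocol and SAP*

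**What the plan says.** **Source and timing.** Section 8.5: "Subjects will be recruited from the Investigators' patient records". Section 8.3: "Eligible subjects will be enrolled at the 24-month follow up timepoint". Section 5 and Tables 1 and 2 give that visit a window of day 700 to day 1,040.

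**Order of events.** Under Section 8.4 the charts are reviewed first, and then "Any patients identified as meeting the study eligibility criteria will then be consented for the study for the prospective observational data collection". Section 8.5 adds that "Eligible subjects will consist of those patients meeting all inclusion criteria and none of the exclusion criteria". Neither section says how patients are to be found or in what order they are approached.

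**Discretion.** One exclusion in the synopsis covers "Ocular pathology which, in the Investigator's judgment, would either place the subject at increased risk of complications, contraindicate washout". It is applied at enrolment, long after the operation.

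**Size.** Section 8.3: "Up to 130 subjects will be enrolled", with at least 50 in each cohort. Section 5.1 allows up to 15 sites. Section 10.1 bases the total on roughly how many eligible patients the sites have, but does not give that number.

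**Who is counted.** Section 10.2 limits the intent-to-treat set to subjects who were both enrolled and treated. Section 8.9.2 counts a secondary IOP-lowering procedure as a treatment failure. Section 9 collects adverse events from surgery up to enrolment. Subject numbers are issued only after consent (Sections 8.6 and 12.2), accountability covers enrolled subjects (Section 12.3), and the investigator records listed in Section 15.2.3 do not name a screening log.

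**The concern.** The study has no control group in which the same selection would cancel out. The responder percentages, the mean IOP change, the secondary-intervention rate and the primary safety endpoint (the rate of sight-threatening adverse events) describe whoever is enrolled. If the person identifying candidates can see two years of pressures, drops and complications, patients who did well may be more likely to be approached, with or without intent. A patient who was re-operated at month 10 and never approached need leave no trace in the study data. Without a count of eligible patients, the final report could neither show nor rule out such an effect, and no later analysis of the enrolled subjects could remove it.

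**Working it through.** **1. How much outcome exists at enrolment.** 700 / 30.4375 = 23.0 months and 1,040 / 30.4375 = 34.2 months. Enrolment therefore falls 23 to 34 months after surgery. That the outcome is in the chart is an inference. It rests on recruitment from the investigators' own records (8.5), on review of those records for medication use and adverse events (8.6), and on collection of adverse events up to enrolment (9).

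**2. Whether any provision closes the gap.**
- Section 8.4 governs patients already identified. It does not say that all treated cases must be identified.
- The cap is 130 over up to 15 sites, or 130 / 15 = 8.7 per site if all take part. No order of approach is given if more are eligible.
- The intent-to-treat definition (10.2), the failure rule (8.9.2) and the retrospective collection of adverse events (9) all begin once someone is enrolled. None reaches a patient who was not.
- No visible section asks for a list of treated cases, a log of non-enrolled patients, or a comparison with them.

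**3. The plan's own figure.** Section 10.1 gives a 97.5% chance of detecting an event of about 3% frequency in 130 subjects. 1 − (1 − 0.03)^130 = 0.981, which agrees with the stated figure, given that the frequency is approximate. It presumes that enrolment is unrelated to having had the event.

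**4. Illustration for responder rates.** Let p be the true responder rate and k the chance that a success is enrolled relative to a failure. Observed rate = pk / (pk + 1 − p). The documents give neither p nor k, so both are assumed. For p = 0.70:
- k = 1.25: 0.875 / 1.175 = 74%
- k = 1.5: 1.05 / 1.35 = 78%
- k = 2: 1.40 / 1.70 = 82%

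Over a range of p:

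| True rate | k = 1.25 | k = 1.5 | k = 2 |
|---|---|---|---|
| 60% | 65% | 69% | 75% |
| 70% | 74% | 78% | 82% |
| 80% | 83% | 86% | 89% |

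**5. Illustration for adverse events.** Let r be the chance that a patient with the event is enrolled relative to one without it (assumed). Observed rate q = 0.03r / (0.03r + 0.97), and the chance of seeing at least one event is 1 − (1 − q)^130.
- r = 0.75: q = 0.0225 / 0.9925 = 2.3%; chance 95%
- r = 0.5: q = 0.0150 / 0.9850 = 1.5%; chance 86%
- r = 0.25: q = 0.0075 / 0.9775 = 0.8%; chance 63%

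**The case against.** **Section 8.4 can be read as an approach rule.** Taken plainly, it sends every patient identified as eligible to consent. A reader might therefore infer either that the plan is silent on whom to approach, or that Section 8.4 settles the matter. Neither holds. The sentence exists and must be credited, but it leaves identification open and does not say what happens when the cap binds.

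**The cap may leave little to choose from.** Section 10.1 ties the size to the patients available, and Cohort A further requires a pre-operative washout with diurnal IOP. If the pool is close to 130, selection has little room. This stands as a limit on the size of the problem. The pool is not stated, so it cannot be used to dismiss the problem; the proposed log would settle it.

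**A rule may sit in text that cannot be seen.** Sections 7.1 and 7.2, part of inclusion criterion 1, text in Section 8.7 and the footnotes to Tables 1 and 2 are not available in the public copy. That has to be conceded. Sections 8.4 and 8.5, where such a rule would naturally appear, are legible and contain none. Section 11 says that site initiation trains staff to select subjects properly and that monitors review charts, but it states no rule for consecutive cases.

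**The study is descriptive.** Section 10.1 says it is not built to test hypotheses. A descriptive rate still needs a known denominator if it is to describe treated patients.

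**Conclusion.** The concern holds in this limited form: a site can follow the visible text exactly and still enrol patients whose good outcome it already knows, and nothing in the data would reveal it. A reader might go further and infer that enrolment is selected on success, or that the reported rates will be inflated. The documents do not support that. They contain no enrolment fractions, no pool size and no evidence of how any site chose. Enrolment is also only one of several influences on the reported rates.

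Under assumed relative enrolment of 1.25 to 2, the illustrated shift in a true 70% responder rate is about 4 to 12 percentage points. Both the 70% and the ratios are assumptions. The same mechanism would lower the observed adverse event rate and weaken the detection assurance in Section 10.1. The conclusion also assumes that the unavailable text contains no enrolment rule and that investigators can see the post-operative course in their own charts. The change should be made, because a cheap procedure would reduce the risk and make it measurable.

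**What to change.** Amend Sections 8.4 and 8.5 as follows:
- Each site lists all OMNI-plus-cataract cases meeting the chart criteria, separately for Cohorts A and B and ordered by surgery date. The list includes patients with secondary interventions or adverse events since surgery.
- Within each cohort, patients are invited consecutively until enrolment to that cohort closes, keeping the minimum of 50 per cohort. Separate lists are needed so that one cohort does not fill the places of the other: 50 + 50 leaves at most 30 of the 130 places free. The rule should not rely on a site allotment, because the visible text defines none.
- Each site keeps a log of listed patients who were not enrolled, with the reason, including use of an investigator-judgment exclusion.
- The final report gives the numbers eligible, approached and enrolled, by site and cohort.
- Where chart use is permitted, enrolled and non-enrolled patients are compared on pre-operative IOP and medications, last post-operative IOP and medications, secondary interventions, and sight-threatening adverse events. The post-operative items are essential, since a comparison at baseline alone could miss selection on outcome.

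Cost: protocol wording, a site log and modest coordinator time. Sample size, visits and clinical care do not change.

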## 8.6 DATA EXTRACTION

Data for the pre-operative) and surgery visits will be collected retrospectively onto case report forms (CRFs). The data collected will be in accordance with Tables 1 and 2 (8.1 & 8.2: Study Schedule).

Following signing of the ICD, a subject ID number will be assigned consisting of a two-digit study identification number, a two-digit site identification number followed by a two-digit subject number ( [REDACTED] ). Subject ID numbers will be assigned sequentially.

Medical records will be reviewed for demographic and medical history information, pre-operative, medication use data, adverse events, and surgical information, including clock hours of canaloplasty and trabeculotomy. Intra-operative complications will be abstracted from the Operative Notes.

## 8.7 PROSPECTIVE VISITS

After obtaining an understanding of the purpose of this study and reviewing and signing the ICD, all subjects will begin the prospective study visits. These visits should be performed according to the schedule provided in Tables 1 and 2. All attempts should be made to conduct each visit within the time interval specified in Tables 1 and 2. Evaluations conducted outside the prescribed time period will be considered protocol deviations.

[REDACTED]

[REDACTED]

### 8.7.1 WASHOUT OF HYPOTENSIVE MEDICATIONS

Subjects who underwent washout prior to OMNI surgery (Cohort A) and who are taking hypotensive medications at the 24- and 36-month visits will be instructed to discontinue their ocular hypotensive medication regimen and to return for a post-washout visit after completing the appropriate washout period.

[REDACTED]

[REDACTED]

If the study subject fails to remember to not use ocular hypotensive medication for the study eye per the required washout period, they can restart washout and return for the

appropriate visit upon completion of washout and as long as it falls within the specified visit window. The minimum wash-out periods are specified in Table 3 below.

**Table 3: Ocular Hypotensive Medication Washout Periods**

Brand Name/Chemical Name	Minimum washout period
Carbonic Anhydrase Inhibitors	
Diamox ® (Acetazolamide) – oral Rx	5 days
Neptazane ® (Methazolamide) – oral Rx	5 days
Azopt ® (Brinzolamide)	5 days
Trusopt ® (Dorzolamide Hydrochloride)	5 days
Muscarinic Agonists	
Salagen, Pilocar (Pilocarpine)	5 days
Alpha Adrenergic Agonist	
Alphagan ® (Brimonidine)	14 days
Iopidine ® (Apraclonidine Hydrochloride)	14 days
Beta Blockers	
Betagan ® (Levobunolol Hydrochloride)	28 days
Betoptic ® (Betaxolol Hydrochloride)	28 days
OptiPranolol ® (Metipranolol)	28 days
Timoptic/Betimol ® (Timolol Maleate)	28 days
Prostaglandin Analogs	
Lumigan ® (Bimatoprost)	28 days
Travatan ® (Travoprost)	28 days
Xalatan ® (Latanoprost)	28 days
Zioptan ® (Tafluprost)	28 days
Vyzulta ® (Latanoprostene Bunod)	28 days
Rho Kinase Inhibitor	
Rhopressa ® (Netarsudil)	28 days
Combined Medications	
Combigan ® (Brimonidine Tartrate/Timolol Maleate)	28 days
Cosopt ® (Dorzolamide Hydrochloride/Timolol Maleate)	28 days
Simbrinza ® (Brinzolamide/Brimonidine Tartrate)	28 days
Rocklatan ® (Netarsudil/Latanoprost)	28 days
Krytantek (Brimonidine Tartrate/ Dorzolamide Hydrochloride/ Timolol Maleate)	28 days
Ganfort (Bitmaprostan/ Timolol Maleate)	28 days
Other	Contact Sponsor

**NOTE: A safety IOP check anytime during the wash-out period may be performed at the Investigator's discretion to ensure subject safety and should be reported as unscheduled visits.**

## 8.8 UNSCHEDULED VISITS

An unscheduled visit will be any visit to the clinical site, other than those specified in the protocol. The Investigator and/or qualified investigational staff will perform the procedures necessary to evaluate the study participant at these visits and will record the visit in the subject's CRF. No specific testing is required.

## 8.9 MANAGEMENT OF IOP

For subject safety, a change in medical therapy may be implemented or additional surgical measures may be performed at any time during the study at the Investigator's discretion in the event it is required. The primary concern of the Investigator and Sponsor at all times is the health and safety of the subjects. Usage of hypotensive medications specifically indicated for prevention of IOP spikes following Nd:YAG capsulotomy and administered for up to 72 hours after Nd:YAG capsulotomy will not be considered rescue therapy.

Medications which have been re-started by the Investigator may be discontinued if the Investigator's judgment is that the target intraocular pressure has been reached and the continued use of some or all of the therapy may not be required. Discontinuation of medications after re-introduction is recommended to be in the reverse order of re-introduction. The rationale for discontinuation should also be documented in the subject's medical record.

A record of all ocular hypotensive medications added, discontinued or changed will be documented on the appropriate CRF for each scheduled visit or on a CRF for an Unscheduled Visit, if necessary.

### 8.9.1 PARACENTESIS

If a pressure rise is observed, a paracentesis may be performed, as necessary. If a paracentesis is performed and there is no protocol-defined adverse event, the paracentesis will be documented in the subject's medical record, the applicable visit CRF, and the Ocular Procedures log. If, however, the paracentesis is performed in conjunction with an AE, then the AE is recorded as such, and the paracentesis is also recorded on the AE CRF as a treatment for the protocol-defined AE (as well as the other CRFs mentioned above).

### **8.9.2 SECONDARY IOP-LOWERING INTERVENTIONS TO CONTROL IOP**

If the subject requires another glaucoma procedure to control their IOP, the subject should continue to be followed according to standard of care until the adverse event resolves or 1-month post-re-intervention, whichever is longer. Following this procedure, the subject should be withdrawn from the study.

Subjects who have had a secondary IOP-lowering intervention will be considered treatment failures for the purpose of the endpoint analyses.

### **8.10 WITHDRAWAL AND DISCONTINUATION**

All subjects have the right to withdraw at any point during the study without prejudice. The Investigator can discontinue any subject at any time at his/her discretion, or if continued participation in the study would result in harm to the subject. All efforts should be made by the Investigator to retain the subject in the study. If a subject withdraws prematurely from the study, a genuine effort must be made to determine the reason(s) the subject discontinued the study. The reason must be recorded in the subject's file and on the Study Exit Case Report Form. A subject may withdraw from the study on his/her own or can be withdrawn by the study investigator for reasons including but not limited to non-compliance, being unresponsive, or no longer qualifying under the protocol. A subject may be withdrawn by the Sponsor for reasons including but not limited to early closure or discontinuation of the study. For every subject that withdraws/is withdrawn from the study prior to completing the study, the study investigator should bring the subject back for a final study visit if possible unless the subject has had a recent visit and, in the Investigator's discretion, does not need a final visit. If a subject cannot be returned for a final study visit, the reason should be documented in the subject's study record.

### **8.11 SUBJECTS LOST TO FOLLOW-UP**

Subjects who do not show up for a follow-up must be contacted to attempt to have them come for the follow-up. For those subjects who cannot be reached, every attempt to contact with the subject should be documented. If a subject misses two consecutive follow-up visits without any contact with the study staff, the subject will be considered lost-to-follow-up unless there is a further communication by the subject.

## **9 ADVERSE EVENTS (AEs)**

Adverse Events are defined below. Adverse events that occur in the eye during the trial must be documented in the subject's records. Date of the event, its severity, treatment (if any) and the assessed relationship of the event to the study device will be recorded

on the Adverse Event CRF. Conditions which exist at the time the subject is enrolled will be considered pre-existing conditions and will not be recorded as adverse events unless they increase in severity during the study. Sites should document any known existing medical and ophthalmic conditions at the time of eligibility determination.

Information regarding adverse events that occurred intra and post-operatively up to enrollment into the study will also be collected.

## 9.1 DEFINITIONS OF AE, SAE, SADE, USADE

Adverse Event	Any untoward medical occurrence in a subject who has been treated with the device that does not necessarily have causal relationship with the treatment.
Adverse Device Effect	Any unfavorable and unintended sign (including an abnormal laboratory finding), symptom, or disease that is possibly related to the study device.
Serious Adverse Event (SAE)	Any untoward medical occurrence that: 
 
• Results in death
 
• Is life-threatening
 
• Requires in-patient hospitalization or prolongs existing hospitalization
 
• Necessitates medical or surgical intervention to preclude permanent impairment of a body function or permanent damage to a body structure
 
• Sight-threatening
 

Unanticipated Adverse Device Effect	Any serious adverse effect on health or safety, any life-threatening problem or death caused by, or associated with a device if that effect, problem, or death was not previously identified in nature, severity, or degree of incidence in the clinical investigational plan; or any other unanticipated serious problem associated with a device that relates to the rights, safety, or welfare of subjects (21 CFR 812.3(s)). Any sight-threatening event, whether listed in the protocol or not, is considered to be reportable as a UADE.

